**Table 3: Dosage Modification Criteria and Guidelines for Management of TASELISIB Related Toxicities**

Toxicity NCI-CTCAE (v 4.0)	Actions
Diarrhea	
Grade 1	
 
• Manage with anti-diarrhealsa.
 
• No dose reduction necessary.
 
• For persistent Grade 1 diarrhea occurring after Cycle 2, recommend evaluation for infectious causes via stool cultureb. For non-infectious diarrhea, consider colonoscopy to evaluate for colitis.
 

Grade 2	
 
• Hold taselisib and initially manage with per institutional standard of care until Grade <math>\leq</math> 1. These include antidiarrhealsa.
 
• Obtain stool culture for infectious workupb Infections (e.g. Clostridium difficile, enteric bacteria, CMV) should be treated with the appropriate antibiotic.
 
• For persistent Grade 2 non-infectious diarrhea lasting longer than 48 hours despite treatment with antidiarrheals, treat with oral corticosteroids (20-40 mg prednisone QD starting dose with taper) or budesonide 9mg PO QD.
 
• If Grade 2 diarrhea occurred after Cycle 2, was a recurrent episode, or improved with corticosteroid treatment, resume taselisib treatment at one dose level lower upon improvement to Grade <math>\leq</math> 1 and after completion of corticosteroid treatment.
 
• If Grade 2 diarrhea occurred before Cycle 2, did not require corticosteroid treatment, and was an initial episode, resume taselisib treatment at the same dose upon improvement to Grade <math>\leq</math> 1.
 
• For Grade 2 colitis, resume taselisib treatment at one dose level lower upon improvement to Grade <math>\leq</math> 1 and after completion of corticosteroid treatment.
 
• If Grade 2 diarrhea does not improve after 48 hours of corticosteroid treatment, a colonoscopy is recommended to evaluate for other causes of diarrhea (e.g., CMV colitis)
 

Grade 3	
First Occurrence:
 
 
• Hold taselisib and initially manage with antidiarrheals.
 
• Obtain stool culture for infectious workup.
 
• For Grade 3 diarrhea or colitis, treat with systemic corticosteroids (prednisone 60-80 mg QD equivalent or solumedrol 16-20 mg IV q 8 h to start). Can increase steroid dosage if diarrhea does not improve.
 
• Concurrent infections (e.g., Clostridium difficile, enteric bacteria, CMV) should be treated with the appropriate antibiotic.
 
• For patients that do not improve upon 48 hours of corticosteroid treatment, a colonoscopy is recommended to evaluate for other causes of diarrhea (e.g. CMV colitis)
 
 
If diarrhea or colitis improves to Grade <math>\leq</math>1 and upon completion of any steroid taper or antibiotic treatment, resume taselisib treatment at one dose level lower.
 
Second Occurrence:
 
 
• Discontinue taselisib
 

Grade 4	
 
• Discontinue taselisib.
 

Rash	

Special considerations	
 
Permanently discontinue for any rash with concurrent signs/symptoms strongly suggestive of a severe Type 1 hypersensitivity or anaphylactic/anaphylactoid reaction, fever, or with painful desquamation or mucosal involvement suggestive of Stevens-Johnson Syndrome/ toxic epidermal necrolysis, or with other life-threatening complications
 

Grade 1	
 
Continue dosing at current dose and monitor for change in severity (consider contacting patient between study visits). Consider prescribing topical steroidsc.
 

Grade 2	
 
Monitor closely for change in severity and hypersensitivity-related systemic symptoms (contact patient weekly between study visits)
 
Consider prescribing topical steroidsc
 
Consider dermatological consultation
 
Consider one or more of the following:               
 
Hold dose until resolution to <math>\leq</math> Grade 1, then resume at next lower dose level
 
Dose reduction
 
Initiation of oral steroid treatment unless contraindicatedd, monitor blood sugar carefully if initiating steroids while continuing taselisib
 
 
 

Grade 3: first event	
 
Hold dose and monitor closely for changes in severity and for hypersensitivity-related systemic symptoms
 
Recommend topical steroidsc
 
Recommend initiating oral steroids unless contraindicatedd
 
Upon resolution to <math>\leq</math> Grade 1, reduce to next lower dose level
 
Consider dermatological consultation
 
Consider obtaining photographs of rash if permitted by local regulations
 

Grade 3: first recurrence after dose reduction	
 
Hold dose and monitor closely for changes in severity and for hypersensitivity-related systemic symptoms
 
Recommend initiating oral steroids unless contraindicatedd
 
Discuss with Protocol Chair if would like to consider restarting at next lower level upon resolution to <math>\leq</math> Grade 1, or permanently discontinue
 
Recommend dermatological consultation, if not already performed
 
Consider obtaining photographs of rash if permitted by local regulations
 

Recurrent Grade 3 or Grade 4	
 
Manage as described above.
 
Discontinue taselisib permanently.
 

Hyperglycemia	
For all grades	
 
Instruct patient to follow dietary guidelines provided by the American Diabetes Association
 
For <math>\geq</math> grade 2, initiate, continue or intensify medication with appropriate anti-diabetic treatment (Note: some oral anti-diabetic drugs are CYP3A inducers or inhibitors and should be used with caution)
 
Metformin is the first antihyperglycemic medication of choice because of the lower risk of hypoglycemia with this agent. Because metformin in some patients may also cause diarrhea and not be well tolerated, other antihyperglycemic medications such as sulfonylureas (e.g., glimepiride, glipizide) can be used. Extra caution should be used with other drugs such as sulfonylureas because of the increased risk for hypoglycemia with these agents. Consultation with an endocrinologist can be helpful in managing hyperglycemia.
 
If Grade worsens start following recommendations for the worsened grade
 

Grade 1	
 
Maintain dose level, check FPG every week for 2 weeks, then continue checking every 2 weeks until resolved
 

Grade 2	
 
Maintain dose, re-check FPG within 24 hours, if no worse than Grade 2, initiate or increase the dose of an anti-hyperglycemic (e.g. metformin)
 
If FPG does not resolve to <math>\leq</math> Grade 1 within 14 days after initiation/ intensifying anti-diabetic treatment: consider endocrine evaluation, consider increasing anti-hyperglycemic therapy further.
 
Dosing with taselisib may either be held or continued per investigator evaluation.
 

Asymptomatic Grade 3	
 
Initiate/increase anti-diabetic treatment, re-check FPG within 24 hours, and if no worse than Grade 3:
 
Hold taselisib until hyperglycemia resolves to Grade <math>\leq</math> 2. Anti-hyperglycemics may be initiated or intensified. Consider endocrine evaluation. After this, taselisib may be restarted at the same dose or a lower dose at the discretion of the treating physician. If another grade 3 hyperglycemia event occurs, the above steps should be followed, but the dose of taselisib must be decreased by one dose level.
 

Symptomatic Grade 3 or Grade 4	
If a fasting patient experiences a symptomatic Grade 3 hyperglycemia event (e.g., blurred vision, frequent urination, excessive thirst) or any Grade 4 hyperglycemia event:
 
 
Taselisib dosing should be suspended until the hyperglycemia resolves to Grade <math>\leq</math> 2.
 
The patient should be managed as per standard care, including implementation of additional glucose monitoring and initiation and/or increase of anti-hyperglycemic therapy. The patient will be discontinued from the study if such therapy fails to control their hyperglycemia. Dosing with taselisib may otherwise resume at a lower dose level and after discussion with the Protocol Chair.
 

Hematologic	
Grade 3	
 
Hold taselisib until resolution to <math>\leq</math> grade 1.
 
If resolved in <math>\leq</math> 7 days, resume taselisib at the current dose level.
 
If resolved in <math>></math> 7 days, resume taselisib at one lower dose level.
 

Grade 4	
 
Discontinue taselisib permanently.
 

Pneumonitis	
Grade 1	
 
CT scans with lung windows and pulmonary function testing including: spirometry, DLCO, and room air O2 saturation at rest. Repeat at least every 8 weeks until return to within normal limits.
 
Administer 100% of taselisib dose. No specific therapy required.
 

Grade 2	
 
CT scan with lung windows. Pulmonary function testing including: spirometry, DLCO, and room air O2 saturation at rest. Repeat at least every 8 weeks until return to within normal limits. Consider a bronchoscopy with biopsy and / or BAL
 
Consider corticosteroids if symptoms are troublesome and infectious etiology ruled out.
 
Reduce taselisib dose by 1 dose level until recovery to <math>\leq</math> Grade 1. Study treatment may also be interrupted if symptoms are troublesome. Patients will discontinue study treatment if they fail to recover to <math>\leq</math> Grade 1 within 28 days.
 
Hold taselisib as long as corticosteroids are being given.
 

Grade 3	
 
CT scan with lung windows and pulmonary function testing including: spirometry, DLCO, and room air O2 saturation at rest. Repeat at least every 6 weeks until return to within normal limits. Bronchoscopy with biopsy and / or BAL is recommended.
 
Oral corticosteroids if infection is ruled out. Taper as medically indicated.
 
Hold taselisib as long as corticosteroids are being given.
 
Hold treatment with taselisib until recovery to <math>\leq</math> Grade 1. May restart study treatment within 28 days at a reduced dose (by one level) if evidence of clinical benefit. Discontinue taselisib if recovery to Grade <math>\leq</math> 1 is not evident within 28 days.
 

Grade 4	
 
CT scan with lung windows and required pulmonary function testing, including: spirometry, DLCO, and room air O2 saturation at rest. Repeat at least every 6 weeks until return to within normal limits. Bronchoscopy with biopsy and / or BAL is recommended if possible.
 
Consider corticosteroids if infective origin is ruled out. Taper as medically indicated.
 
Discontinue treatment with taselisib.
 

Other clinically significant toxicities	
Grade 3	
 
Hold taselisib until resolution to <math>\leq</math> grade 1 and then restart at one dose level lower.
 

Grade 4	
 
Discontinue taselisib permanently.
 

- Suggested antidiarrheals include the following: 1) loperamide (initial: 4 mg, followed by 2 mg after each loose stool, up to 16 mg/day); 2) diphenoxylate and atropine (diphenoxylate 5 mg, four times daily [QID], until control achieved (maximum: 20 mg/day), then reduce dose as needed; some patients may be controlled on doses of 5 mg/day; 3) tincture of opium (6 mg of undiluted opium tincture (10 mg/mL) QID.
- Non-infectious diarrhea can be diagnosed by stool culture with work-up for various enteric bacteria and *C. difficile*. Fecal calprotectin is a possible marker for bowel inflammation. Blood-based CMV PCR test can also be used to detect CMV infection.
- Suggested topical steroids include hydrocortisone 2.5% to face bid, triamcinolone 0.1% or fluocinonide 0.1% cream to body bid.
- Suggested oral steroids include methylprednisolone dose pack or prednisone 60 mg daily followed by a taper (e.g., 60 mg X 2 days, 40 mg X 2 days, 20 mg X 2 days, etc.

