- l Tumor assessment should be performed approximately every 2 cycles (up to -5 days) while on study treatment and at End-of-treatment visit if not obtained within the past 6 weeks. Scans should consist of CT scan of the chest, abdomen, and pelvis and a bone scan at baseline. Subsequent scans should consist of CT chest, abdomen and pelvis, and bone scan if bone metastases were present on the baseline studies. At the end of treatment, all scans (baseline and through disease progression) should be sent on a CD to the Vanderbilt Cancer Imaging Support Laboratory for central review and assessment. See Section 10.5 for details and address.
- m Archived tumor biopsy specimen: 20 unstained slides of archived biopsy block (unstained slides) or fresh tumor biopsy will be requested at the time of enrollment prior to initiation of treatment.
- n Tumor biopsies will only be performed in the phase II portion. A tumor biopsy from a metastatic site will be obtained from patients prior to day 1, at cycle 2 day 14-21, and upon progression of disease. The third biopsy (at the end of treatment) will not be required for patients who are removed from study for reasons other than disease progression. A patient who undergoes a research biopsy procedure for the purpose of this protocol, and in whom inadequate tissue is obtained, is not obligated to undergo a repeat biopsy.
- o See section 9.1. Required only for patients at Vanderbilt and only in the phase II portion. This should be performed prior to tumor biopsy, if possible. If MRI sub-study is not feasible due to scheduling, MRI weight limits, etc., patients may still continue with the remainder of the study.
- p Subjects on the enzalutamide + taselisib arm should begin enzalutamide on day 1 of cycle 1, and taselisib on day 1 of cycle 2.
- q Pill Diary can be found in the packet of supplemental forms.
- r See Section 6.4.2.
- s Phase II only. Biopsy questionnaire should be filled out by the patient on C3D1. Form can be found in the packet of supplemental forms.
- t The cycle 2 day 8 visit is only needed for patients on the combination of taselisib + enzalutamide. Patients on enzalutamide only do not need a visit on this day.

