**1 cycle = 28 days**

All pills were self-administered (by the patients themselves). A pill diary was given to all patients enrolled in the study. The investigator will instruct the patient to take the study drugs exactly as specified in the protocol. Taselisib and enzalutamide were administered on a continuous once daily dosing schedule. To assist in PK assessment, for patients enrolled in the combination arm (phase Ib or II) at Vanderbilt only, taselisib was started on day 1, and enzalutamide was added on day 9.

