### 6.3.1 Taselisib

Taselisib tablets are administered once daily until disease progression or intolerable toxicity. Taselisib administration will begin on C2D1 for patients enrolled on the combination arm (with enzalutamide alone beginning on C1D1). Each dose should be taken with a minimum of 3–4 ounces (90–120 mL) of water with or without food in the morning (before noon). If a dose is missed (not taken by noon), the patient will resume dosing with the next scheduled dose. Missed or vomited doses will not be made up. The occurrence and frequency of any vomiting during a treatment cycle must be noted as an adverse event. Patients should swallow the capsules as a whole and not chew or crush them.

A sufficient number of taselisib tablets should be provided to the patient to last until the next cycle. Patients will be instructed to bring their bottles of study drug and their medication diary with them to each study visit.

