#### 7.2.1.3 *Dermatological Toxicity*

Treatment-related rash, including cases of Grade 3 rash, has occurred in patients who received taselisib. This rash is commonly manifested as maculo-papular with or without pruritus. Incidence rate and severity of rash appear to be dose dependent. The rash has resolved upon holding of taselisib and/or supportive therapy (e.g., topical or systemic steroids). Rash and other dermatological events should be closely monitored, and patients with severe rash should be monitored for associated signs and symptoms such as fever and hypotension that may be suggestive of a systemic hypersensitivity reaction. For severe rash, dosing of taselisib should be interrupted, and patients should be treated with supportive therapy per standard of care. Use of topical antihistamine, as well as topical or systemic corticosteroids, may be considered. Dose delay and modification guidelines for patients who experience rash are outlined in Table 3. Of note, no grade 3 or 4 rashes were noted in the phase Ib portion of this study with dose escalation to 8 mg taselisib. However, in the phase II portion with taselisib at 4 mg, 7 of 8 patients on the combination arm experienced a grade 3 or 4 rash with fever within the first 14 days of treatment. No patients who crossed over from enzalutamide to taselisib + enzalutamide experienced the rash, thus the study is amended so that all patients have a 28 day lead-in with enzalutamide prior to starting taselisib (similar to the cross-over arm). The rash resolved in all patients with IV steroids, antihistamines and supportive care.

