**\*\*Specimens should be mailed to arrive at VUMC from Monday 8AM through Friday 1PM\*\***

### 9.5 Pharmacokinetic Sampling

Pharmacokinetic sampling will occur in the phase Ib portion and in 10 patients in the phase II portion (phase II at Vanderbilt only). PKs for patients in the phase Ib portion: will be obtained on cycle 1, day 8 at: 0-4 hours prior to dose of taselisib and 1, 3, and 6 hours post administration taselisib; on cycle 2, day 15 at: 0-4 hours prior to dose of taselisib and enzalutamide and 1, 3, and 6 hours post administration taselisib and enzalutamide; on cycle 4, day 1, plasma sample should be obtained 0-4 hours before taselisib and enzalutamide administration, and 3 hours post-administration of both drugs.

The first ten subjects on the enzalutamide + taselisib arm at Vanderbilt should initiate taselisib on day 1 and enzalutamide on day 9 to facilitate PKs, which will be done on the first 10 Vanderbilt patients on the combination arm only. PKs in phase II (Vanderbilt only) should be obtained on patients receiving both enzalutamide and taselisib on C1D8, C2D15, and C4D1 at 0-4 hours prior to taselisib and enzalutamide and 2 to 4 hours post treatment. Please see the lab manual for details of collection and for information about shipping the samples.

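### Minor: Table 3 sets the taselisib restart dose after a first, steroid-free grade 2 diarrhea by study cycle number, so under the lead-in its same-dose branch is empty for the combination arm

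*Combined protocol and SAP*

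**What the plan says.** Table 3 requires taselisib to be held for grade 2 diarrhea and then gives two restart rules that depend on the cycle.

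- Same dose: if "Grade 2 diarrhea occurred before Cycle 2, did not require corticosteroid treatment, and was an initial episode, resume taselisib treatment at the same dose".
- Lower dose: if "Grade 2 diarrhea occurred after Cycle 2, was a recurrent episode, or improved with corticosteroid treatment, resume taselisib treatment at one dose level lower".

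The schedule for the combination arm is set elsewhere.

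- Study calendar, footnote p: patients on that arm "should begin enzalutamide on day 1 of cycle 1, and taselisib on day 1 of cycle 2".
- Section 6.3.1: "Taselisib administration will begin on C2D1 for patients enrolled on the combination arm".
- Section 7.2.1.3 gives the reason, an early severe rash, and says "the study is amended so that all patients have a 28 day lead-in with enzalutamide prior to starting taselisib".

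Section 6.6 restarts the cycle count at 1X for crossover patients and lets their taselisib begin as early as C1XD1. Table 2 gives a taselisib starting dose of 4 mg, one reduction to 2 mg, then discontinuation.

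One current instruction disagrees with the lead-in. Section 9.5 says that the first ten combination patients "at Vanderbilt should initiate taselisib on day 1 and enzalutamide on day 9 to facilitate PKs", with phase II sampling on C1D8. Calendar footnote k puts the phase II samples at C2D1, C2D15 and C4D1.

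**The concern.** Study cycle number equals cycles on taselisib only when taselisib starts on day 1 of Cycle 1. The lead-in separated the two counts by one cycle, and the grade 2 diarrhea row still uses study cycles.

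The episodes affected are first episodes that need no corticosteroid, because for these the cycle number alone decides the restart dose. Table 3 moves non-infectious grade 2 diarrhea to corticosteroids once it has lasted more than 48 hours on antidiarrheals, so the affected episodes are mainly short or infectious ones. Because the hold is mandatory, each of them needs a restart dose. At stake are whether the plan states that dose, whether patients with the same taselisib exposure get the same instruction in the combination and crossover schedules, and whether the single available reduction is used earlier than it otherwise would be.

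**Working it through.** **Inputs.** Cycles last 28 days (phase II schema; section 6.6 for crossover). Taselisib starts on C2D1 in the combination arm (footnote p, section 6.3.1) and at the earliest on C1XD1 in crossover (section 6.6). The dose steps are 4 mg, 2 mg, stop (Table 2). The plan gives no figure of its own to reproduce here.

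**Step 1, cycle days.** Cycle c covers days 28(c − 1) + 1 to 28c. Cycle 1 is days 1–28, Cycle 2 is days 29–56, and Cycle 3 starts on day 57.

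**Step 2, taselisib days.** Taselisib day = cycle-count day − s + 1, where s is the day of the first taselisib dose.

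- Combination arm, s = 29. The last day before Cycle 2 gives 28 − 29 + 1 = 0, so there is no exposure. Cycle 2 runs from 29 − 29 + 1 = 1 to 56 − 29 + 1 = 28. Cycle 3 starts at 57 − 29 + 1 = 29.
- Crossover with a C1XD1 start, s = 1. The two counts coincide: 1–28, 29–56, and from 57.

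**Step 3, apply Table 3.** The literal reading takes before and after Cycle 2 to exclude Cycle 2 itself. The split reading puts the boundary at the start of Cycle 2. Entries are days since the first taselisib dose, for a first episode without corticosteroids.

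| Schedule | Reading | Same dose | No stated dose | One level lower |
|---|---|---|---|---|
| Combination | Literal | none | 1–28 | from 29 |
| Crossover, C1XD1 | Literal | 1–28 | 29–56 | from 57 |
| Combination | Split | none | none | from 1 |
| Crossover, C1XD1 | Split | 1–28 | none | from 29 |

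The same-dose window is 0 days in the combination arm on both readings, against 28 days in crossover. The forced reduction comes 57 − 29 = 28 days earlier on the literal reading and 29 − 1 = 28 days earlier on the split reading. The reduction is (4 − 2)/4 = 50%.

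**Step 4, look for a restart dose elsewhere.**

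- Section 6.3 requires reduction for grade 3 or 4 toxicity and is silent on grade 2.
- Section 7.2 sets a lower restart dose when both drugs are held. The grade 2 diarrhea row holds taselisib only.
- Section 7.2.1.4 repeats the hold for grade 2 or worse and asks for close monitoring on resumption, without a dose.
- Section 7.4 lets the investigator reduce at discretion and sends departures from the guidelines to the Protocol Chair.

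None of these states the dose for a first steroid-free episode during taselisib days 1–28 in the combination arm.

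**The case against.** The strongest reply is that little is lost in practice. On the literal reading, a first steroid-free episode in Cycle 2 meets no reduction trigger, so a site that resumes at 4 mg breaks no instruction. This stands. A reader might infer that every such patient must drop to 2 mg from the first taselisib day, but that needs after Cycle 2 to mean from the start of Cycle 2, which Table 3 does not say. The dose is unstated, not withdrawn.

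Second, the silence about Cycle 2 itself is not a product of the lead-in. The crossover row shows the same gap at days 29–56, and it would exist with any day-1 start. This also stands. What the lead-in did was empty the same-dose branch and bring the forced reduction forward by 28 days of exposure.

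Third, there are safety valves. Section 7.4 provides the Protocol Chair route, and section 7.2 allows taselisib to return to its original dose after 28 well-tolerated days. The second of these is written for the case where both drugs were held. They soften the effect but do not supply the rule.

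Three further inferences are tempting and not supported.

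- The documents give no rationale for the row, so nothing can be said about what it was meant to protect.
- Section 6.2.1 says that at Vanderbilt "taselisib was started on day 1, and enzalutamide was added on day 9". This is past-tense text within the phase Ib section, which section 6.2 describes as complete, so it can stand as a record of dosing.
- The grade 1 row ("For persistent Grade 1 diarrhea occurring after Cycle 2, recommend evaluation for infectious causes via stool culture") also uses the cycle number. There the shift only brings a recommended work-up earlier in exposure, with no dose consequence, and no fault is shown.

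**Conclusion.** The point holds as a minor inconsistency in the dosing guidance. For combination-arm patients under the lead-in, Table 3's same-dose branch covers 0 taselisib days. Read literally, days 1–28 have no stated restart dose and 2 mg applies from day 29. If the boundary is put at the start of Cycle 2, 2 mg applies from day 1. Crossover patients at the same early exposure are told to resume at the same dose.

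This assumes that the patient is still on the 4 mg starting dose, that Table 3 is read with the reset cycle numbers in crossover, and that crossover taselisib starts on C1XD1. A start later within Cycle 1X shortens that window day for day.

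Patients treated before the lead-in are outside the point, as are recurrent or steroid-treated episodes, colitis and grade 3–4 events. If section 9.5 were followed, the branch would stay reachable for the first ten Vanderbilt combination patients only.

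The number of patients affected cannot be estimated, because the documents give no rate of first, steroid-free grade 2 diarrhea at 4 mg with enzalutamide. A reader might infer that the clinical benefit rate result is compromised. Nothing in the documents supports that, and no effect on that inference is claimed.

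**What to change.** Restate the two grade 2 diarrhea branches of Table 3 in time from the first taselisib dose, and say that they apply to both the combination and crossover schedules. First episodes without corticosteroids in taselisib days 1–28 resume at the same dose. Days 29–56 are assigned explicitly to one branch. The sponsor should choose which, and may weigh the statement in section 7.2.1.4 that severe steroid-responsive diarrhea usually appears after at least 2 months on taselisib.

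As a separate correction, bring the day-1 taselisib start and the C1D8 sample in section 9.5 into line with the lead-in and with calendar footnote k. Section 6.2.1 and the grade 1 row can stay as they are.

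The cost is wording in one Table 3 row and one paragraph of section 9.5 at the next amendment. No new assessments or data are needed.
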